8.4.2 Multivariate Display of Immunogenicity Endpoints

Data visualization techniques may be used to explore the relationship among immunogenicity readouts. The set of readouts may be based on one of the primary endpoints on the set of primary endpoints, or on immunogenicity endpoints that also include secondary or exploratory endpoints. To understand the relationship between pairs of readouts, scatter plots may be used when the number of readouts is small or for a larger number of readouts, a heatmap showing the degree of correlation between any two pairs. Principal component analysis (PCA) and associated 'biplots' of the scores and loadings are particularly useful to understand associations between readouts, especially when readouts are correlated (84). PCA is a method to reduce the dimensionality of the number of readouts to a smaller set of values (principal components) that are normalized linear combinations of the readouts in such a way that the first principal component accounts for the most variability in the data and subsequent components, while maximizing variability, are uncorrelated with each other. A 'biplot' displays the first and second principal component scores and principal component loadings. The x-axis is the value from the first principal component and the y-axis is the second principal component, where each axis label includes the percentage of variation in the total set of readouts captured by the principal component. The top axis is the first principal component loadings and the right axis is the second principal component loadings. An arrow is drawn for each immunogenicity readout (eg. antibody binding magnitudes) from the origin to the point defined by its first two principal component loadings. The length of the arrow represents the amount of total variation of the set of readouts captured by the given readout. The direction of an arrow conveys the extent to which the variation of a readout is in the direction of the first or second principal component. The angle between two arrows conveys information about the correlation of the two readouts, with a zero-degree angle denoting perfect correlation and a 90-degree angle denoting no correlation. Each arrow on the biplot is labeled by the immunogenicity readout it represents. A biplot is annotated with key metainformation such as the treatment arm (most common application) or a demographic category. Depending on the application, K-means clustering and hierarchical clustering may also be applied for multivariate graphical display of immunogenicity readouts.

8.4.3 Analysis of Multiplexed Immunoassay Data

When a small panel of analytes (eg, ≤ 5) is being assessed in a multiplexed immunoassay, the analysis of response rates and response magnitudes will be evaluated and compared as described under the general approach. When a larger panel is being assessed, two approaches may be considered to evaluate the magnitude and breadth of these responses. First, Magnitude—Breadth (M-B) curves maybe employed to display individual- and group-level response breadth as a function of magnitude. Response breadth of neutralizing antibodies is defined as the average of the log10 nAb titer over the panel of isolates, where titers that are below the limit-of-

detection are set to half of that limit. Response breadth of binding antibodies is similarly defined as the average of the response over the panel of antigens.

8.5 Analyses and data sharing prior to end of scheduled follow-up visits

Any analyses conducted prior to the end of the scheduled follow-up visits should not compromise the integrity of the trial in terms of participant retention or safety or immunogenicity endpoint assessments. In particular, early unblinded analyses by treatment assignment require careful consideration and should be made available on a need to know basis. Interim blinded safety and immunogenicity data should not be shared outside of the SMB, PSRT, the protocol team leadership, the HVTN Executive Management Team, the study product developer, and the study sponsor and/or its designee(s) for their regulatory reporting unless approved by the protocol leadership and the HVTN leadership.

8.5.1 Safety analyses

During the course of the trial, unblinded analyses of safety data will be prepared approximately every 4 months for review by the SMB. Ad hoc safety reports may also be prepared for SMB review at the request of the PSRT. Refer to the process described in the HVTN Unblinding MOP for any requests for unblinded safety data prior to the end of the scheduled follow-up visits.

8.5.2 Immunogenicity analyses

An unblinded statistical analysis by treatment assignment of a primary immunogenicity endpoint may be performed when all participants within any study Part (A, B, or C) have completed the corresponding primary immunogenicity visits and data are available for analysis from at least 80% of these participants. Similarly, an unblinded statistical analysis by treatment assignment of a secondary or exploratory immunogenicity endpoint may be performed when all participants within any study Part have completed the corresponding immunogenicity visit and data are available for analysis from at least 80% of these participants. The Laboratory Program will review the analysis report prior to distribution to the protocol chairs, DAIDS, study product developer, and other key HVTN members and investigators. Reports for distribution or presentation should use PubIDs and not PTIDs for individual responses. Distribution of reports will be limited to those with a need to know for informing future trial-related decisions. The HVTN leadership must approve any other requests for HVTN immunogenicity analyses prior to the end of the scheduled follow-up visits.

9 IMMUNOGENICITY TABLES AND FIGURES, BY ASSAY

9.1 Antibody Dependent Cellular Cytotoxicity (ADCC)

ADCC assay is conducted to address protocol (v3.0) secondary objective 3, that is, to measure Fc mediated antibody effector functions. A subset of serum specimens collected from participants enrolled in HVTN135 are tested to assess response rates and magnitude of serum Antibody Dependent Cellular Cytotoxicity (ADCC). Antibody responses to cells expressing HIV Env is measured with established Luciferase and GranToxiLux (GTL) assays using infant (participant) sera. To quantify maternal immune responses, paired mothers' sera from corresponding visits also tested, even though the mothers do not receive any study product.

ADCC assays are performed on infant participant serum samples collected at visit 1 (cord blood), visit 2 (whole blood), and visit 12 (whole blood). For the analysis, visit 2 is considered as "primary baseline", and visit 1 as an "exploratory baseline". The primary plots and tables will not include visit 1, only visit 2 and 12. Paired maternal serum samples at visits 2 and 12 are also assayed to assess maternal immune response.

As the study participants (infants) are HIV-exposed, the infant baseline responses are expected to be higher than usual due the influence of the maternal immune system. For this reason, visit 2 primary baseline values are not used in response calls, and an assay specific fixed positivity threshold (provided by the lab) will be used instead.

9.1.1 Antibody Dependent Cellular Cytotoxicity (Luciferase)

The antigen analyzed in ADCC Luciferase assay is HIV-1 CH505 IMC. CEM.CCR5.NKR cells infected with HIV-1 CH505 IMC are tested in a 96-well plate for the Luciferase ADCC assay. Participant sera in addition to controls are incubated with the IMC-infected cells and ADCC is detected through the use of Viviren luminescence.

The data from Luciferase assay is semiquantitative. Two definitions of the magnitude of the response are considered: peak of specific killing (definition 1), and area under the curve (AUC) (definition 2). The paired maternal immunes responses are also plotted for comparison, but not included in primary analysis. There is no baseline subtraction applied to the responses, and a fixed positivity threshold is applied to background (plate-level assay background) subtracted percent killing or loss of luciferase activity. A positive response is defined as >=10 after background subtraction of baseline sample and positivity at one of the first dilutions.

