9.1.1.1 List of Tables

- Infant ADCC response rate of peak background subtracted percent killing or loss luciferase activity by treatment group, study visit (v2 and v12), and antigen
- Distribution of peak background subtracted percent killing or loss luciferase activity among all infant participants by treatment group, study visit (v2 and v12), and antigen
- Distribution of peak background subtracted percent killing or loss luciferase activity among infant positive responders only by treatment group, study visit (v2 and v12), and antigen
- Distribution of pAUC (peak AUC) among all infant participants by treatment group, study visit (v2 and v12), and antigen
- Distribution of pAUC (peak AUC) among infant positive responders only by treatment group, study visit (v2 and v12), and antigen

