9.1.2 Antibody Dependent Cellular Cytotoxicity (GranToxiLux or GTL)

The antigen analyzed in ADCC Luciferase assay is Clade B CH505 gp120. CEM.CCR5.NKR cells coated with Clade B CH505 gp120 are tested in a 96-well plate for the GTL assay. Participant sera in addition to controls are incubated with the HIV protein and ADCC detected using granzyme B substrate (GTL).

The data from GTL is quantitative, measuring the percent of Granzyme B (GzB) activity or the percent of antigen-coated target cells positive for GzB. Two definitions of magnitude of response are considered: the peak background subtracted % GzB activity (definition 1), and area under the curve (AUC) (definition 2). The paired maternal immune responses are also tabulated and plotted for comparison, but not included in primary analysis. There is no baseline subtraction applied to the responses, and a fixed positivity threshold is applied to background (plate-level assay background) subtracted %GzB activity. A positive response is defined as >= 8% GzB activity.

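### SAP 9.1.1 gives two incompatible positivity rules for the luciferase ADCC assay, and the sentence that sets the cutoff can be read as subtracting the infant's own baseline.

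*SAP*

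**What the plan says.** SAP 9.1 covers both ADCC assays. It treats visit 2 as the primary baseline and visit 1 (cord blood) as an exploratory one. It then says that "the infant baseline responses are expected to be higher than usual due the influence of the maternal immune system", and that for this reason "visit 2 primary baseline values are not used in response calls". A fixed, assay-specific threshold supplied by the laboratory is to be used instead.

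SAP 9.1.1 (luciferase) repeats this: "There is no baseline subtraction applied to the responses". It goes on to name the quantity that the cutoff acts on: "a fixed positivity threshold is applied to background (plate-level assay background) subtracted percent killing or loss of luciferase activity". The next sentence, which closes the paragraph, reads: "A positive response is defined as >=10 after background subtraction of baseline sample and positivity at one of the first dilutions".

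SAP 9.1.1.1 plans a responder table at both visits: "Infant ADCC response rate of peak background subtracted percent killing or loss luciferase activity by treatment group, study visit (v2 and v12), and antigen".

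The companion assay in SAP 9.1.2 (GTL) has a rule with no baseline term: "A positive response is defined as >= 8% GzB activity". The ICABA rule in SAP 9.2 has none either; it is a 5% cutoff after mock-background subtraction.

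The ADCC response rate two weeks after the fifth vaccination, by flow cytometry and/or luciferase, is part of secondary endpoint 3 (Protocol 5.2, SAP 3.2).

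**The concern.** Two adjacent sentences give different instructions for the same call. The first sets a threshold on killing net of plate background and excludes the infant's own baseline. The second ties the threshold to a subtraction involving the baseline sample.

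The second sentence cannot simply be skipped. It is the only place where the SAP gives the luciferase cutoff, because SAP 9.1 says only that the laboratory provides one. Since the GTL and ICABA rules are free of any baseline term, a programmer could also take the luciferase wording as a deliberate exception.

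All the mothers are HIV-infected, so raised baselines are expected across the cohort. Protocol 6.1.2 expects transplacental and breast-milk antibody to be undetectable by about one year. Subtracting a birth value at visit 12 would then remove activity that is expected to have gone already, and would make the responder call depend on the mother's antibody. That is the dependence SAP 9.1 sets out to avoid.

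**Working it through.** The documents derive no figure from this rule, so there is nothing to reproduce. The check compares the two readings.

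**Notation.** V12 is percent killing at visit 12, net of plate background. B is the same quantity at baseline, taken as zero or more. The cutoff of 10 is from SAP 9.1.1.

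- Reading A (fixed threshold): positive if V12 ≥ 10.
- Reading B (baseline subtracted): positive if V12 − B ≥ 10, that is, V12 ≥ B + 10.

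**Where they differ.** The readings disagree exactly when 10 ≤ V12 < B + 10. The bar under B rises with baseline:

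| B | Bar under A | Bar under B |
|---|---|---|
| 0 | 10 | 10 |
| 10 | 10 | 20 |
| 20 | 10 | 30 |
| 30 | 10 | 40 |
| 60 | 10 | 70 |

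Worked cases (values assumed):

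- B = 30, V12 = 25: positive under A; 25 − 30 = −5, so negative under B.
- B = 30, V12 = 40: positive under A; 40 − 30 = 10, so positive under B.
- B = 20, V12 = 5: negative under both, because V12 is below 10.

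**The planned visit 2 table.** If the baseline is visit 2, the value tested at visit 2 is B − B = 0. Since 0 < 10, every visit 2 response rate is 0% in every arm. If visit 1 were the baseline, this would not follow by construction.

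**Possible size.** The documents give no ADCC distribution, so the following is an illustration under assumptions: B normal with SD 10, V12 normal with SD 12, the two independent, both clipped to 0–100. The means are those before clipping. Response rates at visit 12:

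| Mean V12 | Reading A | B, baseline mean 0 | B, mean 10 | B, mean 20 | B, mean 30 |
|---|---|---|---|---|---|
| 15 | 0.66 | 0.54 | 0.36 | 0.17 | 0.05 |
| 25 | 0.89–0.90 | 0.80 | 0.62 | 0.37 | 0.17 |
| 40 | 0.99 | 0.97 | 0.90 | 0.74 | 0.50 |

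Among simulated infants with B ≥ 20, the response rate under B ran from 0.02 to 0.69 over the scenarios tried.

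**Weight of one call.** Group sizes are from Protocol Table 3-1 and Section 6.1.2. One changed call moves the response rate by:

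- Group 7: 1/5 = 20 points, or 1/4 = 25 points at the planned evaluable n of 4.
- Pooled Groups 3 and 5: 1/18 = 5.6 points, or 1/13 = 7.7 points at the planned evaluable n of 13.

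**The case against.** The strongest answer is that the SAP's intention is clear and the sentence is garbled or left over. SAP 9.1 excludes baseline values from response calls and says why. SAP 9.1.1 repeats that no baseline is subtracted and says what the threshold acts on. The table list speaks of background-subtracted killing, and the GTL and ICABA rules have no baseline term. The disputed phrase is itself ambiguous, since it could mean that plate background is subtracted from the baseline sample. The 0% result at visit 2 also counts against the literal reading, because nobody plans a response-rate table that is zero by design. This argument stands as evidence of intent. It does not remove the conflict, because the sentence with the cutoff still contradicts the sentence before it.

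A reader might infer that the SAP definitely subtracts baseline, and that infants with high maternal ADCC at birth will therefore be called non-responders. The documents do not support that. Misclassification needs the literal reading to be programmed and V12 to lie between 10 and B + 10. A high baseline alone is not enough, as the case B = 30, V12 = 40 shows. Infants with V12 below 10 are negative under either reading; that may describe many placebo recipients if maternal antibody has waned as Protocol 6.1.2 expects.

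The reach is also limited. The two luciferase magnitude measures (peak killing and AUC) are stated to be free of baseline subtraction. The GTL response rate, which also serves secondary endpoint 3, is unaffected. So are the primary immunogenicity endpoints, BAMA and B-cell phenotyping.

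**Conclusion.** The contradiction is real and should be corrected before the luciferase response calls are programmed. SAP 9.1.1 contains two rules that give different responders whenever 10 ≤ V12 < B + 10, and the sentence that carries the cutoff is the one at odds with the rest of the section.

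The consequence is conditional. If the cutoff sentence is coded as baseline subtraction, the luciferase response rate in secondary endpoint 3 can only stay the same or fall (given B ≥ 0). If visit 2 is the baseline, the visit 2 response rates are all zero and carry no information. The fall could be small or large: in the illustration it ranges from 0.99 to 0.97 at one extreme to 0.66 to 0.05 at the other. Those figures rest entirely on assumed distributions and are not a forecast. If the fixed-threshold reading is coded, as the surrounding text suggests it should be, nothing is misclassified on this account.

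**What to change.** Replace the last sentence of SAP 9.1.1 with wording such as: *An infant sample is positive if percent killing (or loss of luciferase activity), net of plate-level background, is at least 10 at one of the first dilutions. No visit 1 or visit 2 value from the same infant is subtracted.*

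Because SAP 9.1 says that the threshold comes from the laboratory, the laboratory should confirm the cutoff of 10 and its unit. It should also say which dilutions count as the first ones, which the SAP does not define. If baseline subtraction was in fact intended, SAP 9.1 and the preceding sentence of 9.1.1 must be changed instead, with a justification, the baseline visit named, and the visit 2 response-rate row dropped where visit 2 is that baseline.

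The cost is one SAP sentence and one query to the laboratory. No sample, assay run or sample size changes.

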9.1.1.1 List of Tables

- Infant ADCC response rate of peak background subtracted percent killing or loss luciferase activity by treatment group, study visit (v2 and v12), and antigen
- Distribution of peak background subtracted percent killing or loss luciferase activity among all infant participants by treatment group, study visit (v2 and v12), and antigen
- Distribution of peak background subtracted percent killing or loss luciferase activity among infant positive responders only by treatment group, study visit (v2 and v12), and antigen
- Distribution of pAUC (peak AUC) among all infant participants by treatment group, study visit (v2 and v12), and antigen
- Distribution of pAUC (peak AUC) among infant positive responders only by treatment group, study visit (v2 and v12), and antigen

9.1.1.2 List of Graphs

- Barcharts of ADCC Luciferase response rates and boxplots of ADCC response magnitudes by treatment group, study visit (v2 and v12), and antigen
- Exploratory figures [all figures include both positive and negative responders and are implemented for both magnitude definitions. All figures are implemented for all vaccine groups combined, and for all placebo groups combined]
 - Scatterplot of infant response magnitude at v1 vs v2 by antigen [this plot helps to justify and inform the use of v1 responses as a substitute for missing v2 responses]
 - Scatterplot of infant response magnitude vs maternal response magnitude at each study visit (v2 and v12) by antigen [this plot informs on whether maternal immune responses are associated with infant immune responses, and potentially informative for isolating vaccine-induced immune responses]
 - Side by side boxplot of infant response magnitude and maternal response magnitude at each visit (v2 and v12) by antigen, with mother-infant pairs connected across the side-by-side boxplot [this plot is an alternative way of visualizing the mother-infant association shown in the last plot]
 - Side by side boxplot of maternal minus infant response magnitude by visit (v2 and v12) and antigen [this plot shows the distribution of the difference in maternal and infant immune responses, i.e., a specific contrast of the two immune responses]

Side by side boxplot of infant v12 minus v2 response magnitude and maternal v12 minus v2 response magnitude by antigen, with mother-infant pairs connected across the side-by-side boxplot [this plot examines whether infant change in immune response is associated with maternal immune response change]

9.1.2 Antibody Dependent Cellular Cytotoxicity (GranToxiLux or GTL)

The antigen analyzed in ADCC Luciferase assay is Clade B CH505 gp120. CEM.CCR5.NKR cells coated with Clade B CH505 gp120 are tested in a 96-well plate for the GTL assay. Participant sera in addition to controls are incubated with the HIV protein and ADCC detected using granzyme B substrate (GTL).

The data from GTL is quantitative, measuring the percent of Granzyme B (GzB) activity or the percent of antigen-coated target cells positive for GzB. Two definitions of magnitude of response are considered: the peak background subtracted % GzB activity (definition 1), and area under the curve (AUC) (definition 2). The paired maternal immune responses are also tabulated and plotted for comparison, but not included in primary analysis. There is no baseline subtraction applied to the responses, and a fixed positivity threshold is applied to background (plate-level assay background) subtracted %GzB activity. A positive response is defined as >= 8% GzB activity.

9.1.2.1 List of Tables

- Infant response rate of peak activity by treatment group, study visit (v2 and v12), and antigen
- Distribution of peak activity among all infant participants by treatment group, study visit (v2 and v12), and antigen
- Distribution of peak activity among infant positive responders only by treatment group, study visit (v2 and v12), and antigen
- Distribution of AUC among all infant participants by treatment group, study visit (v2 and v12), and antigen
- Distribution of AUC among infant positive responders only by treatment group, study visit (v2 and v12), and antigen

9.1.2.2 List of Graphs

- Barcharts of infant peak activity response rates and boxplots of peak activity response magnitudes by treatment group, study visit (v2 and v12), and antigen
- Exploratory figures [all figures include both positive and negative responders and are implemented for both magnitude definitions. All figures are implemented for all vaccine groups combined, and for all placebo groups combined]
 - Scatterplot of infant response magnitude at v1 vs v2 by antigen [this plot helps to justify and inform the use of v1 responses as a substitute for missing v2 responses]
 - Scatterplot of infant response magnitude vs maternal response magnitude at each study visit (v2 and v12) by antigen [this plot informs on whether maternal immune responses are associated with infant immune responses, and potentially informative for isolating vaccine-induced immune responses]
 - Side by side boxplot of infant response magnitude and maternal response magnitude at each visit (v2 and v12) by antigen, with mother-infant pairs connected across the side-by-side boxplot [this plot is an alternative way of visualizing the mother-infant association shown in the last plot]
 - Side by side boxplot of maternal minus infant response magnitude by visit (v2 and v12) and antigen [this plot shows the distribution of the difference in maternal and infant immune responses, i.e. a specific contrast of the two immune responses]

Side by side boxplot of infant v12 minus v2 response magnitude and maternal v12 minus v2 response magnitude by antigen, with mother-infant pairs connected across the side-by-side boxplot [this plot examines whether infant change in immune response is associated with maternal immune response change]

